1.7 Lay summary

Acute lower respiratory tract disease affects large numbers of people worldwide. Older people are more likely to have disease, suffering both reduced quality of life and increased mortality from respiratory infection. Previous studies have tried to define the burden of respiratory infection in adults, but these studies have been limited as they required patients to have either an identified cause of disease (microbiological diagnosis) or change on a Chest X-ray (radiological diagnosis). This has led to an underestimate in disease in adults, because other cases have not been counted.

In 2019, a new virus called SARS-CoV-2 (also referred to as coronavirus) that causes an illness known as COVID-19 emerged and is causing a worldwide pandemic. As the virus is new to humans, people do not have any immunity to it and large numbers of patients are expected to become infected. We do

not understand fully how this virus causes disease, nor the risk-factors for a poor outcome (including death). We also do not understand how this virus interacts with other bacteria and viruses that cause disease in humans. This is important, because if we can determine how these infections interact with each other and the consequences for the patients affected, we may be able to offer better vaccination strategies to prevent disease and treatments to help patients affected. Other diseases we know are important in adult respiratory infection are pneumococcus and RSV (a cold virus). There are potential new vaccines available for use in adults, but as we do not know the true amount of disease caused by these infections, we cannot determine if using these vaccines in adults would be worthwhile.

The Avon CAP study aims to record all patients admitted with respiratory illness at 2 hospitals in the Bristol area. We will gather data that has already been recorded by the clinical teams treating these patients, including demographics, co-morbidities, outcomes and the results of the investigations undertaken by the medical team. Persons with acute respiratory illness will also be offered participation in the consented portion of this study involving additional testing for pneumococcal and RSV infection, which will identify more cases of such infections than routine testing. We will then use these data to accurately define the true amount of disease caused by respiratory illness and be able to determine the subgroups of disease (for example by patient co-morbidity, microbiological and radiological diagnosis) and determine the impact of COVID-19 on respiratory disease.

COVID-19 vaccine was introduced in the UK in December 2020, with individuals called for vaccination by age and risk group (including certain key worker status). This study provides an ideal opportunity to assess how effective these COVID-19 vaccines are in preventing hospitalizations in a “real world” setting. Real world VE estimates from this study can be compared to those from blinded, randomised clinical trials with more limited numbers of participants. The assessment will be a case control study comparing participants who are hospitalised with LRTI and who have been diagnosed with COVID-19 (cases) or have not been diagnosed with COVID-19 (controls) on admission to hospital, or in the 14 previous days, using a method called the test negative design (TND). Almost all the data required for this assessment will be collected as part of the consented study, including COVID-19 disease, vaccination status, and sociodemographic and clinical characteristics of patients from standard-of-care records held by the GP and/or hospital. The only extra information needed will be some details about behaviours during the pandemic which will be collected from some participants via a short questionnaire. These questions may include occupation, household structure, inclusion in any social bubble and use of masks. It is anticipated the COVID VE assessment will continue for 12-24 months depending on vaccine uptake and COVID-19 attack rates during the study.

2 Schedule of activities

Please refer to

Study procedures and **Error! Reference source not found.** sections of the protocol for detailed information on each procedure and assessment required for compliance with the protocol.

Consented Arm

The investigator may schedule visits (unplanned visits) in addition to those listed in the schedule of activities table, in order to conduct evaluations or assessments required to protect the well-being of the participant. Collection of standard-of-care data will be done for all identified LRTD events in study hospitals and entered into the surveillance databases hosted by the Trusts. This will be conducted by appropriate members of the clinical team, and research team members will only have access to pseudonymised data. Sample collection and interview activities shown in bold below will be undertaken for consented participants only by members of the research team.

Table 1. Comprehensive List of Procedures by Visit for Consented-Arm, Including Visit Windows.

Procedure / Assessment ^a	Screening/ Enrolment Visit ^b	Final Assessment/ Vital Status (Data Collection only)	Convalescent Visit ("Serology Subset" Only) ^e	Mortality Assessment (data collection only)
	Visit 1	Visit 2	Visit 3	Visit 4
	Day 1	Day 30	Day 45	Day 365
Visit Window	Within 48 hours of admission	Day 30 to 45	Day 22 to 60^c	Day 365
Screening (surveillance)	X			
Clinical symptoms	X			
Medical History ^c	X	X	X	
Vaccination History	X		X	
CRB-65 and pneumonia severity (PSI) score	X			
Informed Consent	X			
Eligibility confirmation for embedded study	X			
Patient Interview, including approved questionnaires^f	X		X	
Collect urine specimen	X			

Procedure / Assessment ^a	Screening/ Enrolment Visit ^b	Final Assessment/ Vital Status (Data Collection only)	Convalescent Visit ("Serology Subset" Only) ^e	Mortality Assessment (data collection only)
	Visit 1	Visit 2	Visit 3	Visit 4
	Day 1	Day 30	Day 45	Day 365
Collect upper respiratory tract sample for SARS-CoV-2, RSV and other pathogens^d	X		X ^d	
Collect blood specimen^e	X		X	
Obtain residual (scavenged) standard care specimens from clinical laboratory	X	X	X	
Record SOC respiratory specimen testing results	X			
Record SOC blood culture results	X			
Record SOC chest imaging results	X			
Final acute LRTD Illness Diagnosis		X		
Cardiac complications		X		
Vital Status/Mortality		X		X
Hospitalization duration, readmission, & level of care		X		
Collect Research-related Injuries (RRIs)	X	X	X	

Abbreviations: SOC = standard of care; UAD = urine antigen detection assay; RSV= respiratory syncytial virus; RRI = research-related injury; CRB-65 = Confusion, Respiratory rate, Blood pressure, 65 years of age and older.

- Sample collection and interview activities shown in bold above will be undertaken for consented participants only.
- All participants in the consented enhanced diagnostic testing will have confirmation of their eligibility confirmed and be subsequently enrolled at Visit 1 / Day 1.
- At Visit 2 and 3, relevant changes to medical history since the last visit will be documented.
- Respiratory samples will be collected for RSV and other respiratory pathogen testing if such testing has not already been ordered or completed as part of standard-of-care testing. Details on the type and collection process for samples will be included in the laboratory manual. Another respiratory swab will be collected at the convalescent visit, only if the participant experienced a new ARI after hospital discharge.

- e. For those that consent to participate in the Serology subset, a blood sample will be collected for serologic testing. A remnant of an appropriate blood sample from standard of care testing can be used if appropriate for this use per laboratory manual specifications. For this subset of patients, an additional convalescent visit will take place approximately 22–60 days after enrolment for collection of a convalescent blood sample. However, effort should be made to schedule this visit as close to day 42 as possible. If subject has another enrolment qualifying acute LRTD event(s) prior to their convalescent visit, they will have acute serology specimen taken at each enrolment and only one convalescent serology visit will be completed 42 days after last acute specimen was taken.
- f. The applicable covid risk questionnaire will be completed for participants during relevant period, e.g. national lockdowns.

Non-consented arm

Collection of standard-of-care data will be done for all identified LRTD events in study hospitals and entered into the surveillance databases hosted by the Trusts.

Table 2. Comprehensive List of Information to be collected for non-consented arm.

Procedure / Assessment	First Data Collection	Second Data Collection	Third Data Collection
	Admission	Outcomes and Results	Mortality
	Day 1	Day 30	Day 365
Visit Window	Within 48 hours of admission	Day 30 to 45	Day 365
Surveillance	X		
Clinical symptoms	X		
Medical History ^a	X	X	
Vaccination History	X		
CRB-65 and pneumonia severity (PSI) score	X		
Record SOC respiratory specimen testing results	X		
Record SOC blood culture results	X		
Record SOC chest imaging results	X		
Final acute LRTD Illness Diagnosis		X	
Cardiac complications		X	
Vital Status/Mortality		X	X
Hospitalization duration, readmission, & level of care		X	

Abbreviations: SOC = standard of care; UAD = urine antigen detection assay; RSV= respiratory syncytial virus; RRI = research-related injury; CRB-65 = Confusion, Respiratory rate, Blood pressure, 65 years of age and older.

a. At Visit 2, relevant changes to medical history since the last visit will be documented.

2.1 Study type

Avon CAP is a prospective population-based multi-hospital epidemiological study in patients presenting to North Bristol NHS Trust, University Hospitals Bristol and Weston NHS Foundation Trust (hereon referred to as NBT and UHBW). Additional Trusts may be invited to participate as the study progresses, including the Royal United Hospital NHS Trust in Bath. All LRTD events will be included to ensure complete capture of LRTI events, which are the primary focus of the study. Bristol is a single geographical area with multiple hospitals, general practices (GP) and long-term care facilities (LTCF), which provide care to a defined population (the denominator) in that area.

The study collects simple demographic and clinical data on admission of patients to hospital, as well as the results of microbiological and radiological investigations undertaken as standard-of-care investigations in this patient group. Therefore, the study is non-interventional and a surveillance exercise with an embedded consented study (see Section 1.6).

2.2 Patient population

The patients that will be included in the cohort are all adult patients aged ≥ 18 years presenting to NBT and UHBW with clinical features (signs and symptoms) of acute LRTD. This will be determined by assessing all adult patients admitted to these 2 hospitals using the screening algorithm outlined in Section 4.

3 Research questions and objectives

3.1 Primary outcome

To estimate population-based incidence of community-acquired LRTI hospitalizations during and following the COVID-19 pandemic, overall and for community-acquired pneumonia.

3.2 Secondary outcomes

3.2.1 COVID-19/SARS-CoV-2 infection

1. To estimate the population-based incidence rates of COVID-19-related hospitalizations
2. To describe the proportion of LRTI hospitalizations (overall, standard-of-care pneumonia diagnosis, radiologically confirmed CAP only) attributable to COVID-19, both overall and by age/risk stratification
3. To describe demographics, clinical and epidemiological characteristics and outcomes within COVID-19 LRTI and the different subcategories, both overall and stratified by age/risk
4. To describe mortality rate at 30 days after admission to hospital for COVID-19 LRTI and its subcategories, overall and by age group and risk group status
5. To describe the association between COVID-19 and other respiratory pathogens, including but not limited to *S. pneumoniae*, influenza and RSV, both with co- and super-imposed infection and secondary respiratory infection.
6. To describe the length of hospital stay for COVID-19 LRTI hospitalizations and the proportion of COVID-19 admissions involving an ICU stay.
7. To assess whether *S. pneumoniae* LRTI is associated with more severe COVID-19 clinical outcomes (such as requiring invasive mechanical ventilation) among persons hospitalised with COVID-19 infection.

3.2.2 COVID-19 Vaccine Effectiveness

These measures may each be assessed per vaccine brand or manufacturer in the real-world setting. Definitions of exposure categories and details of the planned COVID-19 VE analysis can be found in Appendix 1.

Primary:

To estimate the effectiveness of 2 doses of COVID-19 vaccine (i.e. fully vaccinated) against hospitalization for acute respiratory infection due to SARS-CoV-2 infection by vaccine brand or manufacturer.

Secondary:

1. To describe the effectiveness of only 1 dose of COVID-19 vaccine (i.e., partially vaccinated) against hospitalization for due to SARS-CoV-2 infection by vaccine brand/manufacturer.
2. To describe the effectiveness of ≥ 1 dose of COVID-19 vaccine (i.e., ever vaccinated) against hospitalization for ARI due to SARS-CoV-2 infection by vaccine brand/manufacturer.
3. To determine the effectiveness of current and future COVID-19 vaccinations by COVID-19 variant in real-world settings

Exploratory:

1. To determine the effectiveness of current and future vaccinations against COVID-19, taking into account factors such as patient characteristics, number of doses and dose intervals, timing of doses relative to disease onset, virus variant and other potential confounding factors.
2. To describe further the effectiveness of COVID-19 vaccines against hospitalization for ARI stratified by various patient characteristics (e.g., age, sex, chronic medical conditions, receipt of influenza vaccine, long term care facility residence, time since vaccination and time between doses).
3. To summarize the proportion of hospitalized patients who receive 0, 1, 2 or more doses of COVID-19 vaccine by number of vaccination doses (to update as vaccination program rollout changes)
4. To summarize the time between administration of the first and second dose of COVID-19 vaccine among hospitalized patients who received 2 doses
5. To summarize the time since vaccination with COVID-19 vaccine (most-recent dose) from illness onset
6. To describe demographic and clinical characteristics and disease severity of any COVID-19 vaccine failures
7. To assess the impact of COVID-19 on confirmed subsequent pneumococcal LRTI

3.2.3 *Streptococcus pneumoniae*

1. To estimate the population-based incidence rates of hospitalizations for the following 12 specified LRTI subcategories:
 - a. all LRTI (overall, pneumococcal only, PCV13-type, and PCV20-type);
 - b. any standard-of-care pneumonia diagnosis (overall, pneumococcal only, PCV13-type, and PCV20-type);

- c. any radiologically confirmed CAP (overall, pneumococcal only, PCV13-type, and PCV20-type).
2. To describe the proportion of LRTI hospitalizations (overall, standard-of-care pneumonia diagnosis, radiologically confirmed CAP only) associated with any *S. pneumoniae*, PCV13, PCV20 serotypes and by individual serotypes, both overall and stratified by age/risk condition
3. To describe demographics, clinical and epidemiological characteristics and outcomes within LRTI and its 12 subcategories, both overall and stratified by age/risk condition
4. To determine mortality rate at 30 days after admission to hospital for LRTI (and its 12 subcategories), overall and by age group and risk group status
5. To describe the serotype and frequency and type of antibiotic resistance among *S. pneumoniae* isolates
6. To describe the length of hospital stay for LRTI hospitalizations and the proportion of LRTI admissions involving an ICU stay, overall and by 12 subcategories

3.2.4 RSV Infection

1. To determine the population-based incidence of RSV LRTI hospitalizations both overall and stratified by presence of underlying risk conditions
2. To describe the clinical and epidemiological characteristics and clinical outcomes of RSV-related LRTI hospitalizations both overall and stratified by presence of underlying risk conditions
3. To describe the proportion of LRTI caused by RSV in hospitalized patients both overall and stratified by presence of underlying risk conditions
4. To describe the difference between the population-based incidence of hospitalization, epidemiology, clinical presentation, and outcomes observed in RSV-positive adults versus those with other common respiratory viruses (eg, SARS-CoV-2 and influenza)
5. To determine the pathogen distribution rates of RSV, SARS-CoV-2, and other viral pathogens among adults admitted with congestive heart failure or chronic obstructive pulmonary disease exacerbations

3.3 Exploratory objectives

3.3.1 *S. pneumoniae* exploratory objectives

1. To describe the occurrence of cardiovascular events within 30 days of hospitalization for pneumonia for standard-of-care pneumonia diagnosis and radiologically-confirmed CAP only (overall, pneumococcal only, PCV13-type, and PCV20-type) including the following events: non-ST elevation myocardial infarction (NSTEMI), ST-elevation myocardial infarction (STEMI), cerebrovascular accident, new episode of atrial fibrillation or other significant cardiac arrhythmia; deep venous thrombosis or pulmonary embolism, new or worsening congestive heart failure, and cardiovascular-related death.
2. To describe time trends in population-based incidence rates of pneumococcal-related hospitalizations during and after COVID 19 pandemic

3.3.2 Respiratory syncytial virus exploratory objectives

1. To determine the rates of sero-response to RSV between acute and convalescent serology and the concordance with molecular test results
2. To determine the prevalence of RSV and other viral pathogens in control participants without acute LRTD
3. To compare the frequency of RSV and other viral pathogen detections among enrolled control participants (without acute LRTD) with the frequency of RSV and other viral pathogen detections among LRTD events
4. To describe time trends in population-based incidence rates of RSV hospitalizations during and after COVID 19 pandemic

3.3.3 Patient outcome and risk factors

1. To determine the risk factors for hospitalisation with aLRTD and its disease subsets
2. To determine the risk factors for poor outcomes following hospitalisation with aLRTD and its disease subsets
 - a. stratified by aLRTD and its disease subsets
 - b. stratified by patient risk factor (for example: age, gender, pre-existing risk factors e.g. COPD, pulmonary fibrosis)

4 Research methods

4.1 Study design

Adults with LRTD will be screened using population-level surveillance at study hospitals, and collection of standard-of-care data will be performed on all LRTD events. Patients presenting during the recruitment period of the study, with documented or suspected COVID-19 will fulfil study eligibility criteria, and therefore all references to LRTD also encompass documented or suspected COVID-19 cases who may not otherwise qualify as LRTD. LRTD patients will be offered participation in the enhanced diagnostic testing portion of this study with informed consent, which will involve collection of urine, respiratory, and in some cases blood samples, for additional testing, if necessary, for COVID-19, pneumococcus, and RSV as well as administration of a short patient questionnaire on COVID-related risk behaviours. The pneumococcal testing will include serotype to allow estimation of the proportion of the burden that is potentially vaccine preventable – either by the currently available PCV13 or the anticipated PCV20, which is currently in the final phases of clinical development. Information about the additional pneumococcal, SARS-CoV-2 and RSV infection testing will be integrated with the population-level surveillance data to allow for more accurate population-based estimates of vaccine-preventable pneumococcal and COVID-19 and RSV-related LRTD incidence. The epidemiologic data generated from the study may serve as the baseline for future vaccine effectiveness studies – either for expected PCV20 or investigational RSV and SARS-CoV-2 vaccines that are also currently under development at Pfizer.

Enhanced Diagnostic Testing. Patients who meet all inclusion criteria and no exclusion criteria with informed consent will be enrolled in enhanced diagnostic testing portion of the study. At the time of their enrolment visit, participants will be interviewed (if possible) and a urine for pneumococcal testing and a swab for respiratory pathogen testing will be obtained in all participants (unless refused at time of collection or the patient's clinical status prevents collection, e.g. an anuric participant cannot provide urine). Aliquots from the urine specimens collected from study participants will be frozen and stored for subsequent shipment to Pfizer laboratories for urinary serotype-specific antigen detection (UAD) and BinaxNOW® testing. Additional testing may be conducted on these specimens or portions of these specimens that may be stored at the Bristol Biobank only after obtaining appropriate permissions.

All LRTD events will have additional information collected at 30 days. Additional information on the participants' final clinical diagnosis, vital status, and cardiovascular complications of their current illness (pneumonia patients only) will be collected.

Study duration. The study is expected to enrol for three consecutive years with an option to extend should additional epidemiological data be needed. Yearly or seasonal interim analyses may be conducted.

Serology subset. All participants in the enhanced diagnostic testing group will be offered participation in the serology subset, which will involve the following additional visits/procedures: 1) serology specimen at enrolment visit/V1 (may be salvaged from SOC specimen if appropriate specimen available), and 2) additional in-person visit at Day 42 to collect a blood specimen for convalescent serology and possibly another respiratory pathogen swab (the later only if another intercurrent acute respiratory illness has occurred). Participation will require signature of an annex to the main study informed consent.

UAD and Viral Testing Controls. An additional group of approximately 400 contemporaneous control participants without acute LRTD, comparable by age group and season to subject in the enhanced testing group, will be enrolled participation. These participants will be identified as adults who are:

3. Patients attending outpatient clinics in participating hospitals in specialties other than respiratory or cardiology OR
4. Patients currently admitted at participating hospitals on non-medical wards with no current acute respiratory or cardiovascular conditions.

Control participants will provide urine for UAD and BinaxNOW testing and an upper respiratory swab sample for RSV/respiratory pathogen testing. UAD testing will help inform cut points for UAD positivity in this population.

COVID-19 VE assessment is described in Appendix 1.

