4.4 Patient selection

4.4.1 Screening inclusion criteria

Patients must meet all the following inclusion criteria to be eligible for enrolment:

1. Aged ≥ 18 years of age
2. Patients with illness with following 2 characteristics:
 - a. Acute illness (i.e., present for 28 days or less); **AND**
 - b. Evidence of acute LRTD:
 - i. Patients with current or suspected COVID-19 or previous proven COVID-19 within last 28 days **OR**
 - ii. Clinical or radiologic diagnosis of pneumonia or an acute LRTI **OR**
 - iii. New onset or worsening of ≥ 2 of following 8 LRTD symptoms or clinical findings:
 1. fever ($>38.0^{\circ}\text{C}$) or hypothermia ($<35.5^{\circ}\text{C}$) before or within 24 hours of enrolment;
 2. pleuritic chest pain;
 3. cough (including nocturnal only);
 4. sputum production or purulence;
 5. dyspnea (shortness of breath) including orthopnea or on exertion only;
 6. tachypnea (respiratory rate $\geq 20/\text{min}$) documented by healthcare professional;
 7. abnormal auscultatory findings suggestive of LRTD (e.g., crackles/rales or evidence of pulmonary consolidation including dullness on percussion, bronchial breath sounds, wheezing, or egophony);
 8. radiologic finding that is consistent with LRTD, including pneumonia, and/or acute congestive heart failure (e.g., pleural effusion, increased pulmonary density due to infection, the presence of alveolar infiltrates [multilobar, lobar or segmental] containing air bronchograms, or interstitial oedema).

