4.4.2 Screening exclusion criteria

Patients meeting any of the following criteria will not be included in the study:

1. Any patient who develops signs and symptoms of LRTD after being hospitalized for ≥ 48 hours (either at current hospital, another transferring hospital, or a combination of these), unless admitted with current, previous proven, or suspected COVID-19 infection.
2. Previously enrolled participants readmitted ≤ 7 days after discharge for their study qualifying admission, unless admitted with current, previous proven, or suspected COVID-19 infection
3. At the time of enrolment, an LRTD-related diagnosis has been excluded or another diagnosis confirmed (for example, patient was found to have fever and tachypnoea due to an intraabdominal process such as cholecystitis)

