7.1.1 V1 data collection

Patients meeting screening criteria will have basic demographic and clinical data collected on an e-CRF after consent. This will involve collection of the following data at visit 1:

- Patient details
- Eligibility checks – inclusion/ exclusion criteria components
- Date of hospitalization, length of stay in hospital
- Demographics (age, gender, race/ethnicity, socioeconomic status estimated by postcode, vaccination [e.g. influenza/ PCV13/PPV23/COVID-19 and date of relevant administration], smoking status, alcohol/drug use)
- Details of present illness (symptoms, date of onset, vital signs on admission to hospital)
 - Used antibiotics/antivirals in the 14 days prior to admission
- Standard-of-care test results
 - Routine biochemistry and haematology test results on admission, including C-reactive protein and NT-proBNP
 - Blood cultures
 - Respiratory microbiology testing, including bacterial (eg, PCR and culture) and viral testing (eg, COVID19, RSV and influenza)
 - Pneumococcal testing (eg, BinaxNOW urine test),
 - Antibiotic resistance results for pneumococcal isolates
 - Sputum Gram stain results
 - COVID-19 testing data collection will include tests from up to 14 days prior to hospitalisation based on patient self-report and medical records
- Hospitalization data:

- Admission hospital
- Dates and time of admission/discharge
- ICU stay (yes/no)
- Number of days in ICU
- Mechanical ventilation and days of ventilator use
- Requirement for new/increased haemofiltration
- Non-invasive ventilation requirement and days of usage
- New York Heart Association (NYHA) Heart Failure Classification, Pneumonia Severity (CRB65 and PSI scores)
- Relevant Medical History and Major Comorbidities
- Rockwood Frailty Score and Charlson Comorbidity Index
- COVID risk behaviours questionnaire, which may include occupation, household structure, inclusion in social bubble and mask wearing

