9.2.2 Lower respiratory tract infection

Lower respiratory tract Infection will be defined as enrolled subject with one of the following:

1. Final clinical diagnosis consistent with LRTI (ie, pneumonia or other LRTI); **OR**
2. Positive laboratory test for pneumococcus, RSV, SARS-CoV-2 or any other infectious respiratory pathogen; **OR**
3. Evidence of both:
 - a. Active infection, ie at least 1 of the following conditions: reported fever, reported chills, measured temperature of $>38.2^{\circ}\text{C}$ or $<35^{\circ}\text{C}$, or an abnormal white blood cell count or differential) **AND**
 - b. Lower respiratory tract disease (at least 1 of the following conditions: abnormal breath sounds, documented tachypnea, cough, sputum production, or dyspnea)

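### RSV is to be compared with SARS-CoV-2 and influenza under unequal entry rules: COVID-19 status by itself meets the LRTD criterion and lifts two exclusions, while confirmed RSV or influenza by itself does neither

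*Protocol*

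**What the plan says.** Section 3.2.4, item 4, is a secondary objective. It is to describe differences in hospitalisation incidence, epidemiology, presentation and "outcomes observed in RSV-positive adults versus those with other common respiratory viruses (eg, SARS-CoV-2 and influenza").

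Section 4.4.1 requires an acute illness of at most 28 days (2.a) and evidence of acute LRTD by one of three routes:

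- 2.b.i: "Patients with current or suspected COVID-19 or previous proven COVID-19 within last 28 days"
- 2.b.ii: "Clinical or radiologic diagnosis of pneumonia or an acute LRTI"
- 2.b.iii: "New onset or worsening of ≥ 2 of following 8 LRTD symptoms or clinical findings"

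Section 4.1 states what the first route implies: "therefore all references to LRTD also encompass documented or suspected COVID-19 cases who may not otherwise qualify as LRTD".

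In Section 4.4.2, exclusion 1 (LRTD signs appearing after 48 hours or more in hospital) and exclusion 2 (readmission within 7 days of discharge) both apply "unless admitted with current, previous proven, or suspected COVID-19 infection". Exclusion 3 (LRTD ruled out, or another diagnosis confirmed) has no such exemption.

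Section 9.2.2 classes an enrolled patient as having LRTI on any one of several grounds. One of them is "Positive laboratory test for pneumococcus, RSV, SARS-CoV-2 or any other infectious respiratory pathogen".

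**The concern.** A comparison between viruses is interpretable when each group is drawn by the same rule. Here, LRTD findings or an LRTI diagnosis are the normal condition of entry for RSV and influenza, but not for SARS-CoV-2. Presentation is itself one of the compared features, so symptom frequencies may differ partly because of who was let in. Incidence on the SARS-CoV-2 side includes events of a kind that RSV and influenza contribute only by the suspected-COVID-19 route. Outcomes are averaged over a different mix of patients. Late in-hospital onset and early readmission are likewise admitted for COVID-19 and generally barred for the others.

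Adjusting for age or comorbidity would not cure this, because the missing RSV and influenza patients are not in the data. A reader could take a difference in entry rules for a difference between viruses.

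**Working it through.** **Step 1. Entry conditions side by side** (Sections 4.1, 4.4.1, 4.4.2)

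| Condition | Confirmed SARS-CoV-2 | Confirmed RSV or influenza |
|---|---|---|
| Acute illness, 28 days or less (2.a) | Required | Required |
| Infection by itself satisfies 2.b | Yes, 2.b.i | No |
| Entry by 2.b.ii or 2.b.iii | Open | Open |
| Entry by 2.b.i as suspected COVID-19 | Open | Open |
| Exclusions 1 and 2 | Exempt | Apply, unless admitted as suspected COVID-19 |
| Exclusion 3 | Applies | Applies |

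The rows differ on whether the infection suffices and on exclusions 1 and 2.

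**Step 2. Does a later definition restore balance?** Section 9.2.2 does not. Once a patient is enrolled, a positive test for any listed pathogen is enough for LRTI, so a SARS-CoV-2 patient who entered only by 2.b.i is counted. Section 9.2 requires laboratory confirmation of current infection for COVID-19. That removes patients who were only suspected, but not confirmed patients without LRTD findings. Section 3.2.4, item 4, adds no entry condition of its own.

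**Step 3. What figures are available?** Section 9.1 gives 23,000 patients a year and 630,000 adults. The rate is 23,000/630,000 = 3.65 per 100 person-years. The limits are (23,000 ± 1.96 × √23,000)/630,000 = 3.60 to 3.70, which reproduces the stated interval. This is an all-LRTD figure. The section gives no count by virus or by entry route.

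**Step 4. Effect on incidence.** Let s be the share of SARS-CoV-2 events that enter only through 2.b.i. Of N events, N(1-s) would remain under the rule of 2.b.ii or 2.b.iii. The population denominator is the same, so the inflation factor is N / [N(1-s)] = 1/(1-s). The values of s are assumptions.

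| s | 1/(1-s) |
|---|---|
| 5% | 1.05 |
| 10% | 1.11 |
| 20% | 1.25 |
| 30% | 1.43 |

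Events admitted only through the exemptions from exclusions 1 and 2 come on top of this.

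If a share r of RSV events also enters only by 2.b.i, as suspected COVID-19, the SARS-CoV-2 to RSV incidence ratio is multiplied by (1-r)/(1-s). With s = 20% and, for illustration, r = 5%, that is 0.95/0.80 = 1.19 instead of 1.25. The distortion of this ratio disappears only if r = s.

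**Step 5. Effect on outcomes.** Pooled SARS-CoV-2 mortality is (1-s) × m1 + s × m0, where m1 applies to patients meeting 2.b.ii or 2.b.iii and m0 to the rest. With assumed m1 = 15% and m0 = 5%, it is 14.5%, 14.0%, 13.0% and 12.0% for the four values of s. If m0 exceeded m1, it would rise instead. The protocol gives neither value, so the direction is open.

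**The case against.** **This belongs in the analysis plan.** The objective is secondary and descriptive, and Section 9.3 leaves detailed methods to the SAP. The SAP could well add a restriction, and it is not at hand. But the unequal rule is not a gap: it is written into the eligibility criteria, and the Section 4.1 sentence extends it to every use of the term LRTD. The SAP could not recover RSV or influenza patients who were never enrolled. It could only narrow the COVID-19 side, against the wording of Section 4.1.

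**Broad COVID-19 entry is deliberate.** It serves the incidence of COVID-19-related hospitalisations (Section 3.2.1, item 1). This stands, and nothing here asks for enrolment to change.

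**The affected group may be small.** This also stands. A patient who enters only by 2.b.i is acutely ill, has no pneumonia or LRTI diagnosis and shows fewer than two of eight common findings.

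A reader might also infer more than the documents support:

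- *That RSV or influenza patients without LRTD findings can never enter.* They can, if admitted as suspected COVID-19. In a pandemic that path may be frequent, and it narrows the imbalance.
- *That any incidental SARS-CoV-2 positive is enrolled.* Criterion 2.a and exclusion 3 still apply, and the screening in Section 4.2 keeps out presentations without lower respiratory pathology, such as stroke or cellulitis. Exclusion 3 does not clearly remove everyone who enters only by 2.b.i, however, because Section 4.1 counts COVID-19 as LRTD.
- *That the 9,000 a year between 14,000 and 23,000 in Section 9.1 are SARS-CoV-2 events.* The protocol does not say so, and entry includes suspected cases.
- *That patients entering only by 2.b.i have no cough.* Failing 2.b.iii means fewer than two findings, so one may be present.

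**Conclusion.** The point holds as a structural one. Confirmed SARS-CoV-2 qualifies by itself and escapes exclusions 1 and 2. Confirmed RSV or influenza does neither by itself. Followed as written, Section 3.2.4, item 4, compares viruses under different eligibility, and no definition in the protocol restores a common rule.

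The protocol does not let the size or direction be computed. The incidence factor of 1.05 to 1.43 rests entirely on an assumed s of 5% to 30%, and it is smaller for the RSV comparison if some RSV events entered as suspected COVID-19. The mortality values only illustrate the mechanism. The matter should be corrected, in proportion to what it affects: one named, descriptive secondary comparison.

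**What to change.** 1. For Section 3.2.4, item 4, include an RSV, influenza or SARS-CoV-2 event only if it meets 2.b.ii or 2.b.iii. Filtering SARS-CoV-2 alone would leave in RSV and influenza patients who entered as suspected COVID-19.
2. For the same comparison, apply exclusions 1 and 2 to all groups without the COVID-19 exemption.
3. Report the remaining COVID-19 events separately.
4. Qualify the Section 4.1 sentence so that it does not govern comparisons between pathogens.

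No new data should be needed. Section 7.1.1 already lists "Eligibility checks – inclusion/ exclusion criteria components", and Section 8.1.1 lists the same for the non-consented arm. Symptoms, onset date, vital signs, and admission and discharge dates are also recorded across the two arms. The eCRF should be checked to confirm that it shows whether 2.b.ii or 2.b.iii was met even when 2.b.i was ticked. The cost is a short wording change, one analysis filter and fewer SARS-CoV-2 events in this one comparison. Enrolment and the COVID-19 incidence objective are untouched.
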